## **Appendix 7 - Referrals Protocols**

#### Referrals processes

- Routine referrals
  - Timeframe: within 1-2 weeks
  - $\circ$  CHW recommends that patient seek care and explains why this referral is necessary
  - Patient travels to San Lucas to seek a consult with medical director [name] at San Lucas Mission Hospital (SLMH)
- Urgent referrals
  - Timeframe: within 1-2 days
  - CHW recommends referral to patient, explains rationale and emphasizes that this should occur as soon as possible
  - Patient provided with written referral
  - CHW informs CHW coordinator of urgent referral
  - Patient travels to San Lucas to seek a consult with medical director [name] at San Lucas Mission Hospital (SLMH). Written referral note allows them to skip the queue to be seen by [name]
- Emergency referrals

Version #: 1.0

<sup>16 All three of these vitals criteria are taken from the SIRS/sepsis criteria initially defined in 1992. While the qSOFA score is now recommended for sepsis screening, these older criteria were chosen because they are all objective and can be collected by automated devices (digital thermometer and automatic blood pressure cuff), limiting user error by community health workers. In addition, if any of the three criteria are present, we consider this a positive screen and the application recommends transfer for immediate care. We expect that this will increase sensitivity for detection of systemic infection and/or sepsis

[name]

- Time frame: same day, as soon as possible
- CHW recommends emergency transport to patient
- CHW calls SLMH to arrange for ambulance transport of the patient

# Indications for referrals

- Routine referrals
  - Stage I hypertension (BP 140-160/90-100 mmHg)
  - Non-infected diabetic ulcer
  - Need for renal function testing
  - A1c ≥9 despite maximal doses of metformin and glibenclamide for ≥3 months
  - A1c ≥9 for 3 consecutive checks
  - A1c above glycemic target, but less than 9 for 4 consecutive checks
  - Recent chest pain, moderate risk (2 of 5 points)
  - Blood in stool or possible melena
  - $\circ$   $\;$  Patient has other symptoms not addressed by the program protocols
  - Urgent referrals
    - Stage II hypertension (BP 160-200/100-120 mmHg)
    - Possibly infected diabetic ulcer, no signs of systemic infection
    - Worsening vision
    - FBG detectable, but ≥400
    - o A1c ≥14
    - Patient cannot tolerate minimum doses of metformin and/or glibenclamide
    - Current chest pain, moderate risk (2 of 5 points)
  - Emergency referrals
    - Severe hypertension (BP ≥200/120 mmHg)
    - Fasting blood glucose undetectable high
    - Postprandial/random blood glucose undetectable high with mental status changes
    - Hypoglycemia associated with altered mental status
    - Persistent hypoglycemia despite treatment in the field
    - Current chest pain, high risk (≥3 of 5 points)
    - o Possibly infected diabetic ulcer with signs of systemic infection

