## [name]

- Patients with diabetes in the rural communities have poor access to quality diabetes care. Only 58% of patients are taking medication on a regular basis and only 13% have achieved good glycemic control
- 2. Outreach clinics run by CHWs are disorganized, undersupplied, sporadic, and ineffective
- CHWs lack the experience and training to effectively titrate oral diabetes medications, assess for possible complications, and provide health education for patients
- 4. Patients lack basic diabetes knowledge, particularly regarding self-management

Utilizing the knowledge gained with this needs assessment, established treatment guidelines for diabetes, and the expertise of SLM medical director [name] and the coordinators the SLM CHW program, we developed protocols for the diabetes program, including a smartphone application to allow for algorithmic management. This process was iterative and collaborative and involved our local partners at every step.

In February and March, we trained a group of 10 CHWs, including 5 CHW coordinators (who have more clinical experience and take on a supervisory and training role for less-experienced CHWs) in the basics of diabetes management, program protocols, and the use of the smartphone application we had developed. With close physician supervision, we then beta-tested the use of the application with a small group of patients. Based on this experience, we have further refined the application and program protocols. We now endeavor to implement this program on a wide scale in the San Lucas area to both improve access to care for patients with diabetes and to establish the efficacy, feasibility, and safety of CHW-led, smartphone application-guided diabetes treatment.

CHW training, program protocols, and the algorithmic approaches facilitated by the smartphone application will be described in more detail in the relevant sections of this protocol and its appendices. An overview of study activities is as follows:

- We will train additional CHWs in basic diabetes care, use of point-of-care (POC) testing technology, and use of the smartphone application that will guide their management of patients with diabetes.
- CHWs will recruit patients with diabetes in the rural villages outside of San Lucas to participate in the program.

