- At the enrollment visit, CHWs will use the smartphone application to screen patients for appropriate inclusion in the program, establish glycemic targets, assess current glycemic control with hemoglobin A1c and blood glucose, measure height, weight, blood pressure, and waist circumference, assess for the presence of diabetes complications (diabetic ulcers, angina, diabetic eye disease), administer oral medications (metformin and/or glyburide, known locally by its alternate name glibenclamide) based on a medication dosing algorithm, and provide diabetes self-management education.
- CHWs will meet with patients on a monthly basis to assess medication adherence and for adverse effects, glycemic control (with blood glucose), screen for diabetic complications, refill medications with titration as needed (if experiencing medication adverse effects or blood glucose is significantly above or below treatment goals), and provide further diabetes education. Again, these activities will be guided by the smartphone application. Every 3 months, the monthly visit will also include A1c measurement for a more definitive measurement of diabetes control and to allow for titration of medications. Patients who are identified as having complications or who are not meeting treatment goals despite maximal dosing of metformin and glibenclamide allowed by the algorithm will be referred to SLM medical director [name] for definitive meangement.
- After all visits, including enrollment and monthly visits, [name], in addition to the study investigators, will
  review data for all patients seen, including treatment recommendations made by the application and
  carried out by the CHWs, and make any changes to the treatment plan as needed based on his clinical
  judgement.
- Mean hemoglobin A1c and proportion of patients meeting treatment goals (primary endpoints) will be
  assessed at 6 months and compared to baseline, in addition to a number of secondary endpoints and
  safety measures as described in the relevant sections of this protocol. If possible, patients will also be
  followed out to 12 months with reassessment of primary and secondary endpoints.

Version #: 1.0

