# 8 Study Analysis

### 8.1 Sample Size Determination

For this study, we plan to recruit approximately 150 patients based on the known population of diabetics in the rural communities surrounding San Lucas Tolimán. Of these, we hope to enroll at least 100 patients in the study. Using these numbers, statistical power was calculated using the UCSF online sample size calculators  for a one-group before-after study. The following parameters were used for calculation:

- a = 0.050
- β = 0.200
- SD for outcome = 2.4 (this was the reported pretreatment SD for A1c for a population of 174 indigenous diabetics upon enrollment in a diabetes treatment program in rural Guatemala)
- Within-subject A1c correlation coefficient (rwithin) of 0.928 (this is based on an analysis conducted to determine the accuracy and precision of the A1CNow®+ testing device49, which we are using in our study) Sample size = 100

With this sample size, we will have adequate power to detect an effect size as small as 0.257% A1c and should easily be able to detect more clinically significant differences of 1% A1c or more.

Version #: 1.0

[name]

Another primary outcome will be the proportion of patients meeting treatment goals vs this proportion at baseline. Using the above website, the same parameters for a and  $\beta$ , sample size of 100, and a baseline proportion of patients meeting treatment goals of 13% (this is based on a needs assessment that we conducted as part of this project), we would have 80% power to detect a proportion of 30.2% of patients with good glycemic control (OR 2.896 compared to baseline).

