  - c. Glibenclamide 10 mg  $\rightarrow$  metformin 1700 mg + glibenclamide 5 mg
  - d. Glibenclamide 15-20 mg  $\rightarrow$  metformin 1700 mg + glibenclamide 10 mg
- 10. Taking glibenclamide with hypoglycemia or hypoglycemia symptoms, previous problems with metformin
  - a. Agrees to take metformin
    - i. Glibenclamide 2.5 mg  $\rightarrow$  metformin 850 mg
    - ii. Glibenclamide 5 mg  $\rightarrow$  metformin 850 mg + glibenclamide 2.5 mg
    - iii. Glibenclamide 10 mg  $\rightarrow$  metformin 850 mg + glibenclamide 5 mg
    - iv. Glibenclamide 15-20 mg  $\rightarrow$  metformin 850 mg + glibenclamide 10 mg
  - b. Refuses to take metformin
    - i. Glibenclamide 2.5 mg  $\rightarrow$  MD consult
    - ii. Glibenclamide 5 mg  $\rightarrow$  glibenclamide 2.5 mg
    - iii. Glibenclamide 10 mg  $\rightarrow$  glibenclamide 5 mg
    - iv. Glibenclamide 15-20 mg  $\rightarrow$  glibenclamide 10 mg
- 11. Taking metformin and glibenclamide without problems
  - a. Metformin 500-1000 mg + glibenclamide 2.5-10 mg  $\rightarrow$  metformin 1700 mg + current glibenclamide dose
  - b. Metformin 500-1000 mg + glibenclamide 15-20 mg  $\rightarrow$  metformin 1700 mg + glibenclamide 10 mg
  - c. Metformin 1500-2000 mg + glibenclamide 2.5-10 mg  $\rightarrow$  metformin 2550 mg + glibenclamide current dose
  - d. Metformin 1500-2000 mg + glibenclamide 15-20 mg  $\rightarrow$  metformin 2550 mg + glibenclamide 10 mg
  - e. Metformin 2550 mg + glibenclamide 2.5 mg  $\rightarrow$  metformin 2550 mg + glibenclamide 5 mg
  - f. Metformin 2550 mg + glibenclamide 5 mg → metformin 2550 mg + glibenclamide 10 mg

g. Metformin 2550 mg + glibenclamide 10-20 mg → metformin 2550 mg + glibenclamide 10 mg

12. Taking metformin and glibenclamide, problems with metformin

- a. Agrees to take metformin
  - i. Metformin 500-850 mg + glibenclamide 2.5 mg  $\rightarrow$  metformin 850 mg + glibenclamide 5 mg
  - ii. Metformin 500-850 mg + glibenclamide 5 mg  $\rightarrow$  metformin 850 mg + glibenclamide 10 mg

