- 11. Glibenclamide with hypoglycemia symptoms, previous problems with metformin, took yesterday
  - a. Agrees to take metformin
    - i. Glibenclamide 2.5 mg  $\rightarrow$  metformin 850 mg
    - ii. Glibenclamide 5 mg  $\rightarrow$  metformin 850 mg + glibenclamide 2.5 mg
    - iii. Glibenclamide 10  $mg \rightarrow$  metformin 850 mg + glibenclamide 5 mg
  - b. Refuses to take metformin
    - i. Glibenclamide 2.5 mg  $\rightarrow$  MD consult
    - ii. Glibenclamide 5 mg  $\rightarrow$  glibenclamide 2.5 mg
    - iii. Glibenclamide 10 mg  $\rightarrow$  glibenclamide 5 mg
- Glibenclamide with hypoglycemia symptoms, previous problems with metformin, did not take yesterday → same as #11
- 13. Metformin and glibenclamide without problems, adherent, took glibenclamide yesterday
  - a. Metformin 850 mg + glibenclamide any dose → metformin 1700 mg + glibenclamide current dose
  - b. Metformin 1700 mg + glibenclamide any dose → metformin 2550 mg + glibenclamide current dose
  - c. Metformin 2550 mg + glibenclamide 2.5 mg  $\rightarrow$  metformin 2550 mg + glibenclamide 5 mg
  - d. Metformin 2550 mg + glibenclamide 5-10 mg  $\rightarrow$  metformin 2550 mg + glibenclamide 10 mg
- 14. Metformin and glibenclamide without problems, nonadherent, took glibenclamide yesterday  $\rightarrow$  continue current doses
- 15. Metformin and glibenclamide without problems, adherent, did not take glibenclamide yesterday → continue current doses
- Metformin and glibenclamide without problems, nonadherent, did not take glibenclamide yesterday → continue current doses
- 17. Metformin and glibenclamide, problems with metformin, adherent, took glibenclamide yesterday
  - a. Agrees to take metformin
    - i. Metformin 850 mg + glibenclamide 2.5 mg  $\rightarrow$  metformin 850 mg + glibenclamide 5 mg
  - ii. Metformin 850 mg + glibenclamide 5-10 mg  $\rightarrow$  metformin 850 mg + glibenclamide 10 mg b. Refuses to take metformin
    - i. Metformin 850 mg + glibenclamide 2.5 mg  $\rightarrow$  glibenclamide 5 mg
    - ii. Metformin 850 mg + glibenclamide 5 mg  $\rightarrow$  glibenclamide 10 mg
    - iii. Metformin 850 mg + glibenclamide 10 mg → glibenclamide 10 mg, MD consult
  - c. Metformin 1700 mg + glibenclamide 2.5 mg → metformin 850 mg + glibenclamide 5 mg
  - d. Metformin 1700 mg + glibenclamide 5-10 mg  $\rightarrow$  metformin 850 mg + glibenclamide 10 mg
  - e. Metformin 2550 mg + glibenclamide 2.5 mg  $\rightarrow$  metformin 1700 mg + glibenclamide 5 mg

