- 10. Glibenclamide with hypoglycemia or hypoglycemia symptoms, no previous problems with metformin, nonadherent → same as #9
- 11. Glibenclamide with hypoglycemia or hypoglycemia symptoms, previous problems with metformin, adherent
  - a. Agrees to take metformin
    - i. Glibenclamide 2.5 mg  $\rightarrow$  metformin 850 mg
    - ii. Glibenclamide 5 mg  $\rightarrow$  metformin 850 mg + glibenclamide 2.5 mg
    - iii. Glibenclamide 10 mg  $\rightarrow$  metformin 850 mg + glibenclamide 5 mg
  - b. Refuses to take metformin
    - i. Glibenclamide 2.5 mg  $\rightarrow$  MD consult
    - ii. Glibenclamide 5 mg  $\rightarrow$  glibenclamide 2.5 mg
    - iii. Glibenclamide 10 mg  $\rightarrow$  glibenclamide 5 mg
- 12. Glibenclamide with hypoglycemia or hypoglycemia symptoms, previous problems with metformin, nonadherent  $\rightarrow$  same as #11
- 13. Metformin and glibenclamide without problems, adherent
  - a. Metformin 850 mg + glibenclamide any dose → metformin 1700 mg + current glibenclamide dose
     b. Metformin 1700 mg + glibenclamide any dose → metformin 2550 mg + glibenclamide current dose
  - c. Metformin 2550 mg + glibenclamide 2.5 mg → metformin 2550 mg + glibenclamide 5 mg
  - d. Metformin 2550 mg + glibenclamide 5 mg  $\rightarrow$  metformin 2550 mg + glibenclamide 10 mg
  - e. Metformin 2550 mg + glibenclamide 10 mg → metformin 2550 mg + glibenclamide 10 mg
- 14. Metformin and glibenclamide without problems, nonadherent  $\rightarrow$  continue current doses
- 15. Metformin and glibenclamide, problems with metformin, adherent
  - a. Agrees to take metformin
    - i. Metformin 850 mg + glibenclamide 2.5 mg  $\rightarrow$  metformin 850 mg + glibenclamide 5 mg
    - ii. Metformin 850 mg + glibenclamide 5 mg  $\rightarrow$  metformin 850 mg + glibenclamide 10 mg
    - iii. Metformin 850 mg + glibenclamide 10 mg  $\rightarrow$  metformin 850 mg + glibenclamide 10 mg
    - b. Refuses to take metformin
      - i. Metformin 850 mg + glibenclamide 2.5 mg  $\rightarrow$  glibenclamide 5 mg

[name]

- ii. Metformin 850 mg + glibenclamide 5 mg  $\rightarrow$  glibenclamide 10 mg
- iii. Metformin 850 mg + glibenclamide 10 mg → glibenclamide 10 mg
- c. Metformin 1700 mg + glibenclamide 2.5 mg  $\rightarrow$  metformin 850 mg + glibenclamide 5 mg
- d. Metformin 1700 mg + glibenclamide 5 mg  $\rightarrow$  metformin 850 mg + glibenclamide 10 mg
- e. Metformin 1700 mg + glibenclamide 10 mg  $\rightarrow$  metformin 850 mg + glibenclamide 10 mg

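### Read literally, Appendix 7's two consecutive-check A1c rules refer a patient who stays below 9 at the fourth check but not one who has worsened to 9 or above

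*Combined protocol and SAP*

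**What the plan says.** Appendix 7 (Indications for referrals) lists three routine A1c triggers:

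- a maximal-dose rule: "A1c ≥9 despite maximal doses of metformin and glibenclamide for ≥3 months";
- a faster consecutive-check rule: A1c of 9 or more at three checks running;
- a slower consecutive-check rule: "A1c above glycemic target, but less than 9 for 4 consecutive checks".

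An A1c of 14 or more is an urgent referral. Section 7.1 schedules A1c at baseline and every 3 months, so checks fall at months 0, 3, 6, 9 and 12. Section 7.4.4 assures 6 months of follow-up, with 12 months if funding and staffing permit. Nothing says whether the baseline check counts, or whether a check in one band counts toward the other rule.

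The overview of study activities in Section 2.1 describes referral more simply: patients "not meeting treatment goals despite maximal dosing of metformin and glibenclamide allowed by the algorithm will be referred to SLM medical director". It gives neither an A1c floor nor a time.

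**The concern.** A referral rule should not become less likely to fire because the patient gets worse. The slower rule has a ceiling at 9. A result of 9 or more therefore ends the run of qualifying checks in the lower band and starts a new count of three in the upper band. A patient one check away from referral can lose it by deteriorating.

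This matters because the community health worker acts on what the application recommends, and the application is programmed from these rules. What is at stake is timely in-person assessment of a small group of patients, not the estimate of the program's effect.

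**Working it through.** The plan gives no figure to reproduce here, so the check is a trace of the rules.

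**Inputs.** Checks at months 0, 3, 6, 9 and 12 (Section 7.1), with baseline counted. L = above goal but below 9; H = 9 or more but below 14. The patient has not been on maximal doses of both drugs for 3 months, so the maximal-dose rule is out. By the consecutive-check rules, referral needs HHH or LLLL.

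**Who stays below maximal doses.** In Appendix 11, nonadherent patients on both drugs without drug problems keep their current doses (item 14, both for goal to 9 and for 9 to 14). Patients with metformin problems have metformin reduced (items 15 and 16). Those who cannot tolerate even the minimum dose have their own urgent referral, so the relevant intolerant patients are those held at a reduced dose.

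**Trace.**

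| Course from month 0 | Present rules | Ceiling of 9 removed from the four-check rule |
|---|---|---|
| L L L L | month 9 | month 9 |
| L L L H H | none by month 12 | month 9 |
| L L L H L | none by month 12 | month 9 |
| H H H | month 6 | month 6 |

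In L L L H H, the last three checks at month 12 are L H H and the last four are L L H H; neither rule is met. The earliest HHH would use months 9, 12 and 15, which is beyond the study. If baseline does not count, the same split appears one check later: L L L at months 3, 6 and 9, then referral at month 12 for L and none for H.

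**Other triggers.** The fasting-glucose triggers (400 or above, or a reading too high to measure) and the A1c trigger at 14 do not reach a patient whose A1c is near 9 unless glucose is extreme. For A1c above goal up to 14, the consult rows in Appendix 11 cover patients on glibenclamide 2.5 mg with hypoglycemia who refuse metformin. Appendix 10 has a further consult for a patient with metformin problems, adherent and with high glucose, who refuses metformin: "Metformin 850 mg + glibenclamide 10 mg → glibenclamide 10 mg, MD consult". These rows catch particular patients, not L L L H in general.

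**How many course shapes.** Among courses always above goal that cross 9 at most once, 4 of 8 are unreferred by month 9: LLLH, LLHH, HLLL and HHLL. Two of these are worsening and two improving. By month 12, 2 of 10 remain: LLLHH (worsening) and HHLLL (improving). These count patterns, not patients.

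**Secondary point: Section 2.1 against Appendix 7.** On full doses with A1c between goal and 9, the dosing tables continue treatment with no consult listed: at enrollment "Metformin 2550 mg + glibenclamide 10-20 mg → metformin 2550 mg + glibenclamide 10 mg" (Appendix 8, item 11.g) and at A1c visits "Metformin 2550 mg + glibenclamide 10 mg → metformin 2550 mg + glibenclamide 10 mg" (Appendix 11, item 13.e). The maximal-dose rule needs A1c of 9 or more. That leaves the four-check rule, first met at month 9 if baseline counts (0, 3, 6, 9) or month 12 if not (3, 6, 9, 12).

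**The case against.** The strongest reply is that the ceiling was only meant to separate the slower rule from the faster one, and that no clinician would read it as cancelling a referral. That may well be the intent. The text does not say so, however, and a programmed rule follows its text. If the application already counts any above-target check, only the wording needs correcting.

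The second reply is oversight. Under Physician Oversight (Section 7.4.1), the medical director reviews each visit summary within a week and approves or changes treatment. A routine referral goes to that same person. This stands, and it reduces the problem to a missing automatic prompt for in-person assessment. Adherent patients with glucose above target and no drug problems are also titrated upward, and the maximal-dose rule catches those who reach full doses and remain at 9 or more.

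Three stronger readings might be inferred, and the documents do not support them.

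- **That Appendix 7 breaks a commitment in Section 2.1.** Section 2.1 is an untimed overview that leaves the detail to later sections and the appendices. A patient who stays between goal and 9 on maximal doses is referred, only later. How long to wait is a clinical judgment: Section 7.4.2 (Month 3 Visit) notes that A1c can lag recent improvement, and travel to San Lucas is a known barrier.
- **That a large share of patients near 9 would be missed.** With a stable true A1c of exactly 9.0 and goal 7, the chance of no consecutive-check referral by month 12 comes out at 66% for check-to-check SDs of 0.3, 0.5 and 0.64. That is a peak at the cut-point: at 9.5 it is 5%, 21% and 31%, and at 10.0 it is 0%, 2% and 7%. The calculation holds true A1c constant for a year in a program that retitrates doses. The 0.64 is 2.4 × √(1 − 0.928), from Section 8.1's SD and "Within-subject A1c correlation coefficient (rwithin) of 0.928"; those come from different sources, and reading them together as test-retest error is an assumption.
- **That trial results are biased.** The secondary endpoint counts referrals actually made, and the primary A1c analyses do not use the referral rules.

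**Conclusion.** The point holds as a defect in one stated rule. Below maximal doses, L L L L is referred at month 9, while L L L followed by 9 or more is not referred by an A1c rule at month 9 or month 12 unless A1c reaches 14. This rests on the literal reading and on counting baseline; without baseline, the split moves to month 12.

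The effect is minor. Nothing changes at or before month 6, the only follow-up that is assured. It therefore matters if follow-up runs to 12 months and in the continuing program. The documents do not say how many patients would follow such a course.

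The difference between Section 2.1 and Appendix 7 is a matter of consistency only.

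**What to change.** Remove the upper limit of 9 from the four-check rule in Appendix 7, so that any four consecutive checks above the patient's target trigger a routine referral. Keep the three-check rule at 9 or more as the faster route. State whether the baseline check counts, and make the application logic match.

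For consistency, the medical director should decide what is intended for patients between goal and 9 on maximal doses. Either extend the maximal-dose rule to any A1c above target, or amend the Section 2.1 overview to say that these patients wait for four checks.

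The cost is one or two rule wordings and the matching change to the application, plus a few more routine referrals to San Lucas, where travel is hard (Sections 7.1 and 7.2). Some of these would be improving patients who are still above goal: H L L L and H H L L would both be referred at month 9. The medical director's review can take that into account.
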